7.11.4 PREGNANCY IN THE CLINICAL TRIAL

Women of childbearing potential (WOCBP) are not excluded from the study as long as adequate birth control methods are being utilized. Prior to enrollment in the clinical trial, WOCBP must be advised of the importance of avoiding pregnancy during the trial and the potential risks associated with an unintentional pregnancy. WOCBP and males with partners who are WOCBP will be instructed to practice an acceptable method of birth control (as defined in Section 4.3) for the duration of the study. Male subjects will be counselled to avoid donating sperm after dosing on Day 1 until the final Exit visit.

During the trial, female subjects are to be instructed to contact the Investigator immediately if they suspect they might be pregnant. The study Sponsor must be contacted immediately and a decision will be made regarding continuation of the pregnant woman in the study based upon the circumstances surrounding the pregnancy. Pregnancy is not reportable as an adverse event; however, complications may be reportable. If a female subject or partner of a male subject becomes pregnant during the study, the PI should report the pregnancy to the Medical Monitor within 24 hours of being notified. The Investigator should follow the pregnancy until completion. At

the completion of the pregnancy, the Investigator will document and report the outcome. If the outcome of the pregnancy meets the criteria for classification as an SAE (i.e. postpartum complication, stillbirth, neonatal death, or congenital anomaly) the Investigator should follow the procedures for reporting an SAE.

8 STATISTICAL CONSIDERATIONS

Descriptive summaries will include mean, standard deviation, median, and range for continuous variables and counts and percentages for categorical variables.

8.1 POPULATION FOR ANALYSIS

- Safety Analysis:

All subjects who received at least one dose of treatment will be included in the evaluation of safety of FCA.

- Efficacy Endpoint(s):

The efficacy analysis will be based on an intention-to-treat population (ITT), which is defined as all subjects who received the single dose of treatment and have at least one visit at or after month 2. Month 2 is the first visit on treatment at which lesion area is measured. Per protocol (PP) efficacy analyses will include all randomized subjects who return for Day 150 of follow up.

Safety is the main analysis population for safety endpoints, and ITT is the main analysis population for efficacy endpoints. The assignment of participants to each analysis population will be based on the review of data after the completion of all data collection, monitoring by the clinical research associate and first round of query resolution by data management and prior to database lock.

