 - **Intention-to-treat (ITT) Population:** all enrolled participants who received IVT Fludrocortisone acetate and had at least one efficacy measurement taken after dosing will be included in the ITT population.

Statistics Analyses Safety Analysis

Statistical methods for the safety analyses will be primarily descriptive in nature. Listings and summaries for all safety data will be presented using the Safety Population. Descriptive statistics (mean, SD, median, minimum and maximum) will be calculated for summaries of continuous safety data and frequency counts and percentages (where appropriate) will be calculated for summaries of discrete/categorical safety data.

Safety data, including vital signs, clinical safety labs and adverse events, will be summarised. Change from baseline will be included in summary tables for vital signs and laboratory parameters. All laboratory data will be included in the data listings and all test values outside the normal range will be flagged. Physical examinations will be listed for each participant. Adverse events (AEs) will be coded using the Medical Dictionary for Regulatory Activities (MedDRA), and data will be summarised by System Organ Class and preferred term.

Efficacy Analysis

Exploratory analysis will be performed for the best-corrected visual acuity (BCVA) and will be scored with reference to the Early Treatment Diabetic Retinopathy Score (ETDRS letters). Geographic atrophy lesion size will be measured in mm² by fundus autofluorescence imaging.

Descriptive statistics (mean, SD, median, minimum and maximum) will be summarised for ETDRS letters and GA area in mm² observed values and change from baseline at each post-injection visit. Exploratory analysis of ETDRS letter change and GA lesion size over time will be assessed by using a mixed model. The least squares mean of ETDRS and GA lesion size change from baseline and its 95% confidence interval at each visit will be estimated. Similar analyses will be conducted for intraocular pressures.

Categorical efficacy endpoints such as slit lamp biomicroscopy exam findings, dilated ophthalmoscopy exam findings, colour fundus photography and OCT findings will be summarised descriptively by frequency count and percentage (proportion) as appropriate.

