8.4 ANALYSIS OF SECONDARY ENDPOINTS

The efficacy endpoints are the secondary endpoints of this study, which include complete ocular examination.

ETDRS best-corrected visual acuity (BCVA) will be scored with reference to the Early Treatment Diabetic Retinopathy Study ETDRS letters). ETDRS will be treated as continuous data, and descriptive statistics (mean, SD, median, minimum and maximum) will be summarised for ETDRS observed value and change from baseline at each post-

surgery visit. Exploratory analysis of ETDRS change over time will be assessed by using a mixed model. The correlations between repeated measures of the same participant will be accounted for by the mixed model. The least squares mean of ETDRS change from baseline and its 95% confidence interval at each visit will be estimated. Similar analyses will be conducted for intraocular pressures. Categorical efficacy endpoints such as slit lamp biomicroscopy exam findings, dilated ophthalmoscopy exam findings, color fundus photography and OCT finding will be summarised descriptively by frequency count and percentage (proportion) where appropriate.

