8.6 SAMPLE SIZE

The study is planned to enrol up to 12 participants with geographic atrophy secondary to age-related macular degeneration with visual acuity (20/32 to 20/2000, Snellen's equivalent), following the 3+3 method.

The sample size chosen for this study was selected without formal statistical justification, but the numbers chosen are considered adequate for assessing the study objectives. The sample size was determined on the basis of practical and logistical considerations and not based on statistical power with regard to hypothesis testing or precision with regard to parameter estimation.

This phase 1 trial was designed to identify any important limiting toxicities and to determine if this dose is suitable for phase 2 trial. This was also designed to minimize the likelihood that a minimum number of subjects will be exposed to the investigational drug.

This is an open label study, and no randomization is conducted in this study.

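### The Section 8.1 ITT set requires attendance at Month 2 or later, so the measured IOP, visual acuity and eye-examination summaries can omit an early leaver, contrary to the Synopsis and to either imaging schedule

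*Protocol*

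**What the plan says.** Section 8.1 defines ITT as the subjects who received the single dose and "have at least one visit at or after month 2. Month 2 is the first visit on treatment at which lesion area is measured"; the second sentence of that quote is the reason given for the condition. It then assigns the sets: "Safety is the main analysis population for safety endpoints, and ITT is the main analysis population for efficacy endpoints".

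Section 8.4 decides which variables fall under ITT: "The efficacy endpoints are the secondary endpoints of this study, which include complete ocular examination". It describes there the analyses of ETDRS acuity and IOP (descriptive statistics and a mixed model). It also names slit-lamp, dilated ophthalmoscopy, colour fundus photography and OCT findings as categorical efficacy endpoints, summarised by count and percentage. Section 8.7 says that missing data will generally not be imputed.

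The Synopsis has a different rule: dosed participants who "had at least one efficacy measurement taken after dosing will be included in the ITT population". It has no Month 2 condition.

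The per-protocol set in Section 8.1 reads: "Per protocol (PP) efficacy analyses will include all randomized subjects who return for Day 150 of follow up". Section 8.6 states that "no randomization is conducted in this study".

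**The concern.** Membership of the Section 8.1 set depends on something that happens after dosing, namely attendance about two months later. The variables assigned to that set include the ones by which the protocol itself judges ocular harm. Section 6.2 defines dose-limiting toxicity by inflammation, raised IOP, loss of 15 or more letters, or haemorrhage within 28 days. Section 9.7 gives the DSMB criteria on IOP change, letter loss and inflammation. Anyone who leaves early, for any reason, takes all their post-dose IOP, acuity and examination records out of the planned summaries. If leaving is related to a poor ocular outcome, the summaries look better than the experience of the people dosed. This is a drug not previously given intravitreally to humans (Section 2.3.3), in about nine participants.

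The protocol also has two ITT definitions. Section 8.1 assigns participants to sets after data collection is complete, in an open-label study. The choice between the definitions could therefore be made with outcomes known.

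**Working it through.** The plan states no dropout rate, power or precision figure, so there is no figure of its own to reproduce. The check compares the definitions with the schedule and then works out what one exclusion does.

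**Inputs.** Post-dose visits on Days 1, 7, 14, 28, 60, 90 and 150, each ±1 day (Section 1.2). Cohorts of 3 at 1 mg and 6 at 2 mg, total 9 (Synopsis; Section 8.6 says up to 12, which would change the denominators). Toxicity window of 28 days (Section 6.2). Month 2 is read as the Day 60 visit.

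**1. The two ITT definitions.** Section 8.1 needs a dose plus attendance at Month 2 or later. The Synopsis needs a dose plus one post-dose efficacy measurement. BCVA is scheduled on Day 1 in both Section 1.2 and Section 6.3.3. A participant measured on Day 1 and gone by Day 30 is therefore in under the Synopsis and out under Section 8.1.

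**2. The stated reason against the schedules.** Section 1.2 has FAF at every visit, so the first post-dose lesion image is on Day 1. Section 6.3 lists FAF only at screening (6.3.1) and at termination, Day 150 (6.3.5); it lists none on Day 1 (6.3.3) or on Days 7 to 90 (6.3.4). Month 2 is not the first lesion measurement under either. Under Section 1.2 the condition discards usable images. Under Section 6.3 it admits people who have no post-dose lesion image.

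**3. Timing.** The earliest Month 2 visit is Day 60 − 1 = Day 59, which is 59 − 28 = 31 days after the toxicity window closes. Four of the seven post-dose visits (Days 1, 7, 14, 28) come before it. This is not the share of data lost: anyone who attends Month 2 keeps all earlier records. It is what an early leaver may already have contributed. Colour fundus photography is a partial exception, since Section 1.2 first schedules it after dosing on Day 60.

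**4. Effect of one exclusion.** Suppose one participant has an abnormal slit-lamp finding and makes no visit at or after Month 2. Exact (Clopper-Pearson) 95% limits:

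| Group | All dosed | Section 8.1 ITT |
|---|---|---|
| 1 mg | 1/3 = 33% (0.8% to 90.6%) | 0/2 (upper limit 84.2%) |
| 2 mg | 1/6 = 17% (0.4% to 64.1%) | 0/5 (upper limit 52.2%) |
| Both | 1/9 = 11% (0.3% to 48.2%) | 0/8 (upper limit 36.9%) |

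If two of six are affected and both leave, 2/6 = 33% becomes 0/4.

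For acuity, assume that one of six at 2 mg loses 20 letters and leaves after Day 28, with the other five unchanged. The Day 28 mean change is (−20 + 5 × 0)/6 = −3.3 letters in all dosed participants and 0/5 = 0 in the Section 8.1 set. The reported minimum goes from −20 to 0.

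**5. Chance that it happens.** If each participant independently leaves before Day 59 with probability p (assumed), P(at least one excluded) = 1 − (1 − p)^n.

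| p | n = 6 | n = 9 |
|---|---|---|
| 5% | 26% | 37% |
| 10% | 47% | 61% |
| 20% | 74% | 87% |

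These are chances of any exclusion, whether or not the person had an ocular problem.

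**The case against.** A reader might infer that patients with early toxicity vanish from the ocular safety results. The protocol does not support that. The primary endpoint is local and systemic treatment-emergent events (Section 3.2.1). Section 8.1 puts all dosed subjects in the safety evaluation. Section 8.3 reports all safety data on that set, with AEs by severity and relationship, SAEs, and AEs leading to discontinuation. Inflammation or an IOP rise recorded as an AE stays in numerator and denominator. Neither the toxicity review (Section 6.2) nor the DSMB review (Section 9.7) uses the ITT set. All of this stands.

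Toxicity by itself also removes nobody. Treatment is one injection, so there is no dosing to stop, and Section 7.10.3 has events of special interest followed to resolution. That stands too, but routes out remain: participants may withdraw at any time (Section 7.11.3.1), and after an event of special interest the sponsor decides on further participation (Section 7.10.3). An early termination visit before Month 2 would not meet the Section 8.1 condition.

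It can also be said that visit summaries already give minimum and maximum, so a single extreme value would show. That is true for a participant in the set, not for one excluded from it. No count of participants with vision loss is planned in Section 8.4, so the acuity effect is on the mean and range.

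AE reporting is not a complete backstop. Section 7.11.3 says that unequivocal AMD progression is not recorded as an AE, and that vision loss from progression need not be one. For a loss judged to be progression and too small for the 15-letter criteria, the acuity summary may be the only tabulated trace.

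Finally, read literally, the per-protocol set is empty. That is a wording slip rather than a loss of data: the intended members are evidently dosed participants, and Section 8.4 assigns no analysis to the set.

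**Conclusion.** The point holds for the measured ocular summaries only. Sections 8.1 and 8.4 together make IOP, BCVA, slit-lamp, ophthalmoscopy and OCT results conditional on a visit at Month 2 or later. Fundus photography falls under the same rule, with little practical effect given its schedule. The rule contradicts the Synopsis, and its reason is wrong under both versions of the FAF schedule. The size is one participant at a time, which here means 1/6 to 0/5 or 1/3 to 0/2.

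The conclusion assumes that Section 8.1 governs over the Synopsis, that Month 2 means the Day 60 visit, and that someone leaves before Day 59. The protocol gives no rate for that, so 5% to 20% is only a range for illustration. If the Synopsis definition governs, a participant with any post-dose efficacy measurement is kept and the exclusion does not arise. The contradiction should be settled before outcomes are known. The AE-based primary safety result is not affected.

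**What to change.** - Summarise IOP, BCVA and the eye-examination and imaging findings in the Safety Population (all dosed), and say so in Sections 8.1 and 8.4.
- For GA lesion size and the other efficacy analyses, use the Synopsis ITT definition in Section 8.1, and delete the sentence about Month 2 being the first lesion measurement.
- Reconcile the FAF visits between Section 1.2 and Section 6.3. Which visits carry FAF is for the sponsor to settle.
- Define the per-protocol set on dosed rather than randomised participants.
- Optional: tabulate each participant's highest IOP and worst BCVA change.

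The population changes cost only wording in the protocol and any analysis plan, with no extra visits, participants or measurements. They should be made before database lock, and preferably before outcomes are reviewed for population assignment.

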8.2 DEMOGRAPHIC AND BASELINE CHARACTERISTICS

Participant demographic and baseline variables (age, sex, ethnicity, race, height, weight, and BMI) will be summarised with descriptive statistics. Sex, ethnicity, and race will be summarised with frequency counts and percentages. Baseline ocular assessments will be summarised descriptively as well.

Pregnancy test results, concomitant medication and medical history data for each participant will be presented in data listings. Concomitant medications will be summarised descriptively by using frequency counts and percentages.

8.3 ANALYSIS OF PRIMARY SAFETY ENDPOINTS

No formal inferential statistics will be performed on safety assessments. Statistical methods for the safety analyses will be primarily descriptive in nature. The Fludrocortisone acetate 1mg/0.1mL and 2mg/0.1 mL injection will be considered as safe and tolerable based on the number of subjects presenting severe AEs related to the study drug. It is understood that safety is a medical judgment that cannot be prospectively defined in detail. However, as general guidance, a subject will be considered to have tolerated a dose if the subject experiences no clinically significant drug-related adverse event or laboratory abnormality. Conversely, a subject will not be considered to have tolerated the dose if he experiences a clinically significant drug-related adverse event or laboratory abnormality during the study drug administration or post-administration follow-up period.

Listings and summaries for all safety data will be presented using the Safety Population. Descriptive statistics (mean, SD, median, minimum and maximum) will be calculated for summaries of continuous safety data and frequency counts and percentages (where appropriate) will be calculated for summaries of discrete/categorical safety data.

Adverse events (AEs) will be coded using the Medical Dictionary for Regulatory Activities (MedDRA), and data will be summarised by System, Organ, Class and preferred term. The number and percent of participants reporting each AE will be summarised descriptively (n=9). A participant with two or more AEs within the same level of summarisation (i.e., system, organ, class or preferred term) will be counted only once in that level. The number of AEs reported will also be presented. Adverse events will also be summarised by severity as well as relationship to study treatment. A by-participant AE data listing, including verbatim term, preferred term, system organ class, severity, and relationship to study treatment, will be provided. Separate listings will be generated for SAEs and AEs leading to study/treatment discontinuation.

All haematology, blood chemistry and urinalysis (continuous variables) parameters will be summarised using descriptive statistics for all study visits assessed, including change from baseline (last pre-surgery value) for all post-surgery assessments. All laboratory data will be included in the data listings and all test values outside the normal range will be flagged.

All vital sign parameters will be summarised using descriptive statistics by study visit, including change from baseline (last pre-surgery) for all post-surgery assessments.

Individual vital sign assessments will be listed for each participant. Findings of physical examinations will be listed for each participant and summarised descriptively by using count and percentage by study visit.

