1.1 SYNOPSIS

Title:	A Phase 1b, study of safety and tolerability of Intravitreal Fludrocortisone acetate (FCA in Patients with Geographic Atrophy (GA)
Sponsor:	Eye Co Pty Ltd
Protocol Number, Version and Date:	EC-FCA-001/ Version 1.3 / 22 January 2020
Investigational Product, Dose and Route of Administration:	Fludrocortisone acetate (FCA) 1mg/0.1ml & 2mg/0.1ml Intravitreal (IVT) injection
Rationale for dose:	
Single dose of 0.1 ml in a concentration of 1mg/0.1 mL and 2mg/0.1mL was selected based on previous pre-clinical model (Kivilcim et al). There were no signs of retinal toxicity on slit-lamp examination, indirect ophthalmoscopy, or by light microscopy in all eyes injected with 400µg/0.1mL, 1mg/0.1mL and 2mg/0.1mL. However, it was reported 1 case of intravitreal haemorrhage in 4 mg/0.1 mL.
 
Systemic injection of Fludrocortisone acetate has serious mineral corticoid and glucocorticoid side effects such as hypertension, potassium loss, Cushingoid changes, etc. Intravitreal injection fludrocortisone acetate may avoid systemic side effects.

Objectives:	To determine safety and tolerability of a single dose intravitreal (IVT) injection of 1mg/0.1mL and 2mg/0.1mL FCA in subjects

with GA secondary to Age-Related Macular Degeneration (AMD).

Study Population: Study population will comprise of patients with GA secondary to AMD in both eyes with no previous treatment. The study is planned to enrol up to 9 participants.

Study Design: This study is planned to enrol 9 participants to assess dose escalation based on a 3+3 algorithm. Enrolment will stop if > 2 patients experience dose-limiting toxicity at any time during the study. Dose-limiting toxicity is defined by intraocular inflammation, elevated IOP, reduced vision (loss of ≥ 15 letters), or haemorrhage within 28 days after injection.

Part 1 involves a single participant to assess safety and tolerability of 1mg/0.1mL FCA. This participant will be followed for up to 28 days and reviewed by a safety review committee prior to the recruitment of a further 2 participants treated with 1mg/0.1mL FCA totalling in 3 participants in the first cohort.

Part 2 involves a single participant to assess safety and tolerability of 2mg/0.1mL FCA. This participant will be followed for up to 28 days and reviewed by an independent safety review committee prior to the recruitment of a further 5 participants treated with 2mg/0.1mL FCA totalling in 6 participants in the second cohort.

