3.2 STUDY ENDPOINTS

3.2.1 PRIMARY SAFETY ENDPOINT

To demonstrate safety and tolerability of IVT injections of Fludrocortisone acetate based upon the mean change in GA lesion size as measured by Fundus Autofluorescence (FAF).

- Number and severity of local and systemic treatment emergent adverse events.
-

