6.2 SUBJECT ENROLLMENT

It is the responsibility of the investigator to ensure that subjects are eligible to participate in the study prior to enrollment and throughout the study. Documentation of the personally signed and dated informed consent of each subject, using the study-specific ICF, is required before initiating the Screening process. After written informed consent has been obtained and eligibility to participate established, investigative site personnel will obtain the subject's identification number. Only eligible subjects will be allocated to the open label FCA 1 mg/0.1mL or 2mg/0.1 mL.

Enrollment will occur in two parts in order to minimise the likelihood that subjects will be exposed to risks. During part 1 & 2, subjects will be screened one by one as only one patient will initially be enrolled during part 1 of the trial. The first enrolled subject will participate in a screening period of up to 14 days and a follow-up period of 28 days, to detect an IOP response.

After first subject has completed the follow-up of 28 days after FCA 1mg/0.1 mL injection, The subject's safety data will be reviewed the safety data of this will be reviewed by an independent safety review committee to determine whether to commence enrolment of additional 2 patients in the first cohort of 1mg/0.1mL dose of FCA. Enrolment will be stopped if >2 patients experience limiting-toxicity adverse event related to the study drug. If no more than two adverse events considered to be related to the study drug occur with limiting toxicity, the second cohort will be recruited. Dose-limiting toxicity is defined by intraocular inflammation, elevated IOP, reduced vision (loss of ≥ 15 letters), or haemorrhage within 28 days after injection.

Part 2 will take in place if the 3 subjects have tolerated well the dose. Part 2 initially involves a single subject treated with 2mg/0.1mL FCA to assess safety and tolerability. This subject will be followed for up to 28 days and reviewed by an independent safety

review committee prior to the recruitment of a further 5 subjects treated with 2mg/0.1mL FCA totalling in 6 subjects in the second cohort.

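### Section 8.3 attaches a dose-level 'safe and tolerable' verdict to a count of severe related AEs without a cut-off or uncertainty bound, and 3 and 6 patients cannot support that verdict even with zero events

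*Protocol*

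**What the plan says.** Section 8.3 of the protocol opens its account of the primary safety analysis with "No formal inferential statistics will be performed on safety assessments", and describes the methods as mainly descriptive. It then says of the two doses that the "injection will be considered as safe and tolerable based on the number of subjects presenting severe AEs related to the study drug". No cut-off, tolerable rate, margin or confidence limit is attached.

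Two qualifications follow in the same paragraph. Safety is called a medical judgment that cannot be fully defined in advance. As general guidance, a subject has tolerated the dose if no clinically significant drug-related adverse event or laboratory abnormality occurs in that subject.

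The cohort sizes are in the Synopsis (Section 1.1): "totalling in 3 participants in the first cohort" at 1 mg and "totalling in 6 participants in the second cohort" at 2 mg. The Synopsis also says that the total of 9 rests on practical grounds and not on power or precision. Section 8.6 repeats that disclaimer and describes the trial as "designed to identify any important limiting toxicities and to determine if this dose is suitable for phase 2 trial".

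**The concern.** A descriptive safety analysis is normal in a small Phase 1b study. The difficulty is that Section 8.3 goes beyond description: it announces a positive conclusion about each dose and names a count as its basis, without saying which count leads to the conclusion or how uncertain that count is. Readers of the final report could not tell whether the label had been earned, because nothing in the plan says what would have withheld it.

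The label also has a use. Section 8.6 ties the trial to the decision on Phase 2, and Section 2.3.3 says the drug has not been given intravitreally in humans before. If the report states that a dose was safe and tolerable because few or no severe related events were seen in 3 or 6 people, later planners may take that as evidence about the event rate. The sample carries very little such evidence.

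**Working it through.** The protocol gives no alpha, tolerable rate or confidence bound for safety, so there is no figure of its own to reproduce. The only check is 3 + 6 = 9, which agrees with the Synopsis total.

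**Inputs**
- n = 3 at 1 mg and n = 6 at 2 mg (Section 1.1).
- Event: a participant with at least one severe AE related to study drug (Section 8.3).
- Confidence level: not in the protocol. 95% is assumed here, and both one-sided and two-sided limits are shown.

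**Step 1: the best possible result.** With 0 events in n, the exact (Clopper-Pearson) upper limit U solves (1 − U)^n = a. So U = 1 − a^(1/n), with a = 0.05 for a one-sided 95% limit and a = 0.025 for a two-sided 95% interval.

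| Result | One-sided 95% | Two-sided 95% |
|---|---|---|
| 0/3 | 1 − 0.05^(1/3) = 63.2% | 1 − 0.025^(1/3) = 70.8% |
| 0/6 | 1 − 0.05^(1/6) = 39.3% | 1 − 0.025^(1/6) = 45.9% |
| 0/9, doses pooled | 1 − 0.05^(1/9) = 28.3% | 1 − 0.025^(1/9) = 33.6% |

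**Step 2: one event.** Here U solves (1 − U)^n + nU(1 − U)^(n−1) = 0.05. The one-sided limits are 86.5% for 1/3 and 58.2% for 1/6.

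**Step 3: how often a clean result occurs by chance.** P(0 events) = (1 − p)^n. The protocol states no relevant rate, so these values of p are assumptions.

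| Assumed true rate p | n = 3 | n = 6 |
|---|---|---|
| 10% | 0.90^3 = 73% | 0.90^6 = 53% |
| 20% | 0.80^3 = 51% | 0.80^6 = 26% |
| 30% | 0.70^3 = 34% | 0.70^6 = 12% |

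At a true rate of 20%, about half of all 3-patient cohorts would show no event.

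**Step 4: sensitivity to the other sample size.** Section 8.6 gives up to 12 participants, which does not match the Synopsis. If 12 meant six per dose (an assumption), the one-sided limit after zero events would be 39% at each dose. Pooled over 12 it would be 1 − 0.05^(1/12) = 22%. The conclusion does not depend on which total applies.

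**The case against.** The strongest reply is that the protocol is open about its limits. It calls the safety analysis descriptive, disclaims precision, and says in the same paragraph as the verdict that safety is a medical judgment. Dose-limiting toxicity criteria (Section 6.2), adverse events of special interest (Section 7.10.3) and the monitoring board's criteria (Section 9.7) also inform the safety review. Intervals for small AE counts are often left to the statistical analysis plan, which is not shown.

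Much of this stands. The judgment is not a count alone, and descriptive reporting without tests is acceptable. But the subject-level guidance defines when a person tolerated the dose, not when a dose is safe. The toxicity and monitoring-board criteria govern escalation and continuation, not the final label. A later plan could add an interval, but the verdict and its stated basis are fixed in the protocol text.

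Three stronger readings are tempting and are not supported:
- *That the protocol treats zero events as proof of safety.* It never says so, because it sets no cut-off. The zero-event figures show only the best case that the verdict could rest on.
- *That Section 3.2.1 makes the same claim.* Its phrase "To demonstrate safety and tolerability of IVT injections of Fludrocortisone acetate" continues by basing this on mean change in atrophy lesion size, not on AE counts. That is a different matter.
- *That Section 6.2 claims one patient can establish an IOP rate.* The words "a follow-up period of 28 days, to detect an IOP response" say what the first subject's follow-up looks for. They make no claim about a population rate.

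Nor is it fair to say that safety receives no intervals while efficacy does. Section 8.4 extends the mixed model with 95% intervals to intraocular pressure. What lacks an interval is the AE proportion on which the verdict rests.

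**Conclusion.** The point holds as a defect of wording and criterion in Section 8.3. The section promises a dose-level conclusion, does not say what result would justify it, and uses samples that could not justify it. With no events, the data remain compatible with true rates up to 63% at 1 mg and 39% at 2 mg (one-sided 95%), or 71% and 46% (two-sided 95%). Any observed event raises these limits.

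The figures assume the planned cohorts of 3 and 6, independent patients, and a 95% level that the protocol does not itself specify. They do not suggest that either dose is unsafe, and they are no argument for a larger trial. The point concerns what the trial may claim at its end. It is a worthwhile, inexpensive correction and not a flaw in how the trial is conducted.

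**What to change.** In Section 8.3, replace the sentence that carries the verdict with text such as: *For each dose, the number and proportion of participants with at least one severe AE related to study drug will be reported with the exact (Clopper-Pearson) one-sided 95% upper limit. The conclusion will be stated as the highest rate not excluded by the data, alongside the medical judgment of safety.* A two-sided interval serves equally well, provided that the sidedness is stated.

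So that the paragraph does not contradict itself, change its opening statement on inferential statistics to: *No hypothesis tests will be performed; exact confidence limits are descriptive.*

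The sample size and Sections 3.2.1 and 6.2 need no change for this point, and no clinical threshold is proposed. The cost is two sentences of protocol text, one extra column in the AE table, and a safety statement that looks less favourable than a plain label.
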